CHW Recruitment: We will hire and train 6 CHWs (3@VA, 3@BH), from local patient support organizations (Veteran Service Organizations and BH volunteer office, as we have done in prior CHW studies) to implement the toolkit strategies. CHW employment opportunities announcements will be created. Requirements will include: 1) evidence of a leadership role in the patient community through social support or advocacy organizations; 2) strong communication and interpersonal skills; and 3) a high school education or GED. CHW candidates will not be required to have a background in health. Personal experience with DM will not be required.

CHW Training: We will train the CHWs in key DM concepts, motivational interviewing, brief action planning, and stages of behavior change. CHWs will participate in a 105-hour core competency training developed collaboratively developed by [name] and her team and the Community Health Worker Network of New York. CHWs will conduct mock telephone counseling calls with trained standardized patients to enhance skills, gain feedback, and develop confidence in these techniques. In addition to these training experiences, CHWs will have letter templates, motivational interviewing scripts, and protocols available for patient outreach to standardize and guide patient outreach

CHW Intervention

At each wave's outset, ~ 250 patients at each study site will be randomly selected for outreach and paired with one of five CHWs (2 at BH, 2 at VA, 1 at both clinics). Researchers will provide each intervention group PC provider their selected list of prediabetic patients. PCPs will be asked to review the list to identify anyone they think should be excluded from the intervention. Patients are matched to a CHW according to the patient's language and neighborhood of residence, as the study aims to cluster CHWs' patients to facilitate CHW travel and expertise in local resources. We mail selected patients a letter on behalf of their PCP alerting them of their DM risk status, available prevention resources, and introducing them to their assigned CHW. CHWs will then call patients to describe the program and seek verbal informed consent to enroll in the study. Patients who decline participation will be asked if they are willing to be invited again in subsequent waves of the study. CHWs will continue outreach until they have met their caseload for the wave.

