We developed a toolkit of strategies for pre-DM coaching outreach to standardize the intervention across CHWs and to focus on evidence-based strategies for preventing DM. The toolkit was adapted from the version we developed and used in the PROVE study aiming to improve outcomes in HTN and smoking. The toolkit interventions reflect standards of care and can be selected and tailored for the broad population of pre-DM patients. We will enhance uptake and effectiveness of services by employing CHWs to regularly contact, counsel, remind, and follow-up with patients. Outreach strategies will be tailored to patients' health care needs and their stage of activation. CHWs will deliver outreach based on patient preferences and activation level, as there is evidence that the fit between an intervention and a patient's motivations, beliefs and perceptions encourages activation, goal setting and ultimately behavior change. During their first contact with patients, CHWs will use a standardized, 6-item questionnaire (PAM-6) to quickly assess patients' activation level. Thus, CHWs will offer toolkit strategies that best fit the patients' level of activation, matching patients with the most intensive intervention they are ready to accept. Standardized protocols will also be used to ensure that CHWs dedicate sufficient time to engaging patients with lower levels of activation.

Within the 3-year intervention period, each patient's 12-month CHW intervention will consist of a 6-month intensive phase followed by a 6-month maintenance phase, as described below.

- *Phone Call:* CHWs will call eligible pre-DM patients and ask to obtain informed consent (in accordance with our waiver of documentation of consent) to participate in the study, fully describing the study and reviewing all elements of consent. If the patient consents, CHWs will conduct the intake process, which includes a survey, the PAM, and a conversation about health goals. CHWs encourage the patient to engage in the most intensive strategy that is matched to their activation level and health goals (Health Action Plan).

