- *Telephone-Based Coaching:* CHWs will offer a minimum of 6 monthly, 30-minute phone counseling sessions to all patients using motivational interviewing (MINT) and brief action planning (BAP). However, patients will be offered more frequent coaching, up to once per week. BAP is a counseling approach emphasizing goal setting and MINT principles that can be completed in short telephone counseling sessions.

Telephone coaching will be timed to occur just before or after PC visits to optimize the value of the visit for DM prevention. For patients with lower activation scores (Stages 1 and 2), who are less engaged in their own care, CHWs will prepare patients for PC visits, empowering them to ask questions, seek information and participate in decision-making. This approach can increase PAM scores and help patients to have more effective

encounters with their health care teams and to improve health outcomes such as HbA1c among patients with chronic illnesses.

- CHWs will re-call patients, who are not yet ready to engage in behavior change during the initial phone call, every 6 months unless they ask to be taken off the re-call list.
- *Referral to VA's MOVE! Program or BH's Healthy Lifestyles Program*: These programs offer a series of weekly workshops (BH 8 weeks, VA 12 weeks) focused on healthy eating and exercise. Patients “graduate” after 6 months but then continue with maintenance activities and ongoing peer support. CHWs will also encourage VA patients to participate in Tele-MOVE!, which provides daily interaction with in-home messaging technologies, and clinician contact as needed.
- *Referral to the DM Prevention Program (DPP)*: The DPP is a 16-session, weekly lifestyle intervention with certified DPP coaches, which is effective in preventing DM onset in pre-diabetics. The intensive program is then followed by monthly maintenance phone workshops with the DPP coach. This program will be provided by the study to all patients who wish to participate. These programs are offered by the NYCYMCA and by other community-based organizations.
- *Metformin*: Although not commonly used for DM prevention, metformin has been shown to prevent DM among patients with pre-DM, particularly those struggling with making lifestyle changes or with a BMI > 30. CHWs will suggest that such patients with normal renal function (GFR > 50%) discuss this option with their PCP and will provide a list of these patients to the team.

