- *Maintenance*: After 6 months of intensive coaching, CHWs will transition to making monthly phone check-ins with patients for another 6 months to reinforce the knowledge and behaviors taught earlier.

Data Collection

Patient Data

As a pragmatic, population-based trial, we aim to understand the impact of our interventions on panels of patients in a real clinic environment and therefore will not collect any clinical data directly from patients. Instead we will rely on measurements taken during regular clinic visits and recorded in the EMR. We will access this clinical and administrative data for VA patients through the VA Informatics and Computing Infrastructure (VINCI), a secure, high performance interface with VA's Corporate Data Warehouse (CDW), and for BH patients from the NYC Health and Hospitals CDW. Relying on routinely collected clinical data does have its challenges. Patients in our cohort at baseline may not return to the clinic at appropriate intervals, and there may be incorrect information within the EMR limiting our ability to assess the impact of the interventions on all patients. Learning from our previous work, we will mitigate these challenges by updating the study registry regularly, and validating our data during Phase I of the study as we construct the pre-DM registries.

We will have the CHWs administer a survey (in person or by phone) of all intervention patients to assess patient activation and self-reported behaviors (diet and exercise habits). We will survey each wave's cohort of intervention patients twice: at baseline and at the end of their 1-year intervention phase. Surveys will include an MTA MetroCard worth \$11 to incentivize response. Non-responders will be mailed up to two reminders. A statement will be included with the survey outlining the number of times the survey will be conducted (two), the timeframe for the surveys (now, and one year from now).

Implementation Research

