We will use a similar generalized linear mixed-effects modeling for the secondary outcomes, to explore the relationship of the intervention's effectiveness to specific patient and provider or team characteristics. We will investigate interactions between the intervention and the patients' level of activation, co-morbidities (HTN, depression, and smoking), and health care utilization. We will also test the correlation (Pearson's r) of provider self-efficacy and team collective-efficacy on patient outcomes. We will conduct secondary analyses to better understand the impacts of the individual components of this complex set of interventions. While designed to test the effectiveness of an overall strategy, we will seek to determine which of the intervention elements and dose of intervention (e.g. number of phone contacts, number of mailings, successful referral to *MOVE!*, Healthy Lifestyles, DPP or other programs) were most strongly associated with any improved outcomes. We will also conduct subgroup analyses to see which subgroups may benefit more from the intervention than the others. Such group analyses are data dredging; they should be considered as exploratory analyses and any resulting findings should be confirmed by independent studies.

Because control patients are not surveyed, follow-up survey data for a given wave will serve as the control group for the following wave's baseline survey data. For example, wave 1 follow-up data will be compared against wave 2 baseline data. The data collected in the survey are secondary outcomes.

Attrition/missing data: Although the retention of patients with specific provider panels is relatively stable at the VA and BH, there are a number of reasons for changes including moving, entering a nursing home or rehab facility, not being seen in PC for >2 years, or requiring specialty-based PC. Patients seldom switch among teams or providers within teams, limiting the potential for contamination between study groups. In our VA study of panel management (PROVE), only 7% of 9,841 hypertensive patients switched teams over 12 months of follow-up. In the event that a provider changes teams and moves from one study arm to the other, patients of theirs already enrolled in the study will remain in the study arm in which they were enrolled. In waves after a

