A waiver of consent has been requested. Informed consent is given when a provider chooses to participate in the intervention. He or she can opt out of the study at any point. With regard to surveys, completion of the survey will serve as implied consent. The survey cover sheet includes all elements of consent. Informed consent is implied by patients completing and returning a mail-based survey. Similar to the staff survey, all patient surveys will state that the survey is voluntary, all data will be reported in the aggregate, and completion of the survey serves as consent for participation. The survey will also specify that completion of the survey will not impact their health care in any way and that their individual responses will not be shared with members of their health care team.

Further, patients will be considered to have given informed consent by choosing to continue to interact with CHWs. Patients can request to not be contacted by a team's CHW at any point. This will be clearly stated on all materials given to staff and patients. Interventions will consist of educating patients of existing services at the institution or outside of the institution that they can access to improve their health, ensuring coordination and follow-up on referrals already made by their health care team. Patients interested in attending a institution-provided service (such as MOVE, smoking cessation classes, or Telehealth) will be referred as a part of usual care from their team. Programs such as YMCA DPP are available to anyone that meets pre-diabetes criteria, not just our subjects. Anyone is able to join these programs without the referral of a physician. The study team will only offer existing evidence-based services already available to pre-diabetics. Patients interested in attending the community based DPP will be provided contact information or a warm transfer by telephone, but will need to register themselves and consent to the outside program. PHI will not be sent to either organization by the study team. Patients will be making an informed decision to join such groups and will be explicitly explained this via phone or letter. This same implied consent applies to patients who register for VA's Telehealth or MOVE services and BH's Healthy Lifestyle services.

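### CHWs who deliver the coaching also take the 12-month activation and behaviour survey, so any effect of answering to a familiar coach cannot be separated from the intervention effect

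*Combined protocol and SAP*

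**What the plan says.** - **Who asks, and when.** Data Collection, Patient Data: "We will have the CHWs administer a survey (in person or by phone) of all intervention patients to assess patient activation and self-reported behaviors". The survey is given to each wave's "cohort of intervention patients twice: at baseline and at the end of their 1-year intervention phase".
- **Baseline.** The CHW Intervention section puts the first survey on the consent call: "If the patient consents, CHWs will conduct the intake process, which includes a survey, the PAM, and a conversation about health goals". It also says: "During their first contact with patients, CHWs will use a standardized, 6-item questionnaire (PAM-6) to quickly assess patients' activation level".
- **Pairing and contact.** Patients "will be randomly selected for outreach and paired with one of five CHWs". After intake, "CHWs will offer a minimum of 6 monthly, 30-minute phone counseling sessions to all patients", with more frequent coaching available. Six months of monthly check-ins follow.
- **Comparator.** Control patients are not surveyed. Under Analysis: Patient Clinical Outcomes and Health Behaviors, "wave 1 follow-up data will be compared against wave 2 baseline data".
- **Status of the outcome.** That section classes survey data as secondary. The opening of Data Analysis and Data Monitoring nevertheless places higher PAM scores among the primary hypotheses.
- **Mode.** Data Storage and Confidentiality refers to paper surveys sent back by patients, and the consent section describes a survey returned by mail. Both sit uneasily with CHW administration in person or by phone.
- **Confidentiality.** The consent section says the survey will tell patients that "their individual responses will not be shared with members of their health care team".

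**The concern.** PAM, diet and exercise are self-reports, so the answers can depend on who is asking. At intake the CHW is new to the patient. At 12 months the interviewer belongs to the team that has spent up to a year encouraging the behaviours being asked about, and may be the very person who did so. A difference between 12-month and first-contact answers could reflect real change, a change in how patients answer a familiar coach, or both.

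At stake are the patient-activation and health-behaviour aims, one of which is also listed as a primary hypothesis. The problem is distinct from the absence of surveyed controls. Surveying controls would not remove it if intervention patients still answered to their coach, and a simple within-patient change from baseline carries it too.

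**Working it through.** **1. The plan's own figure (Statistical Power and Sample Size).** 72 patients per CHW × 3.5 full-time equivalents × 4 waves = 1,008. The outreach figure agrees: 2,100 × 0.80 × 0.60 = 1,008. Intervention patients per wave: 72 × 3.5 = 252. The plan gives no effect size, SD or power for PAM or the behaviour items, so there is no survey figure to reproduce.

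**2. Available comparisons.** Four waves give three pairs of follow-up against next baseline, because wave 4 follow-up has no later baseline. At most this is 3 × 252 = 756 per side.

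**3. Interviewer familiarity against exposure.**

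| Survey | CHW contact offered beforehand | Exposed to intervention? |
|---|---|---|
| Baseline, own or next wave | None; taken at intake | No |
| 12 months | At least 6 sessions of 30 minutes, then 6 monthly check-ins: 12 or more | Yes |

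By design no surveyed group has exposure without prior CHW contact, or prior contact without exposure. The t-tests and mixed models therefore have nothing from which to estimate the two separately. The missing-data sensitivity analysis addresses a different question.

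**4. Illustration of scale.** Assume no true effect, a two-sided 5% test (the plan does not state sidedness), SD = 1, and a shift of b SD at follow-up due only to the interviewer. Clustering and differences between waves are ignored.

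SE = √(2/n); P(significant) = Φ(b/SE − 1.96) + Φ(−b/SE − 1.96).

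For n = 252, SE = √(2/252) = 0.089. At b = 0.2, b/SE = 2.245 and P = Φ(0.285) + Φ(−4.205) = 0.61.

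| Patients per side | b = 0 | 0.1 | 0.2 | 0.3 |
|---|---|---|---|---|
| 252 (one pair) | 5% | 20% | 61% | 92% |
| 164 (one pair, 65% response) | 5% | 15% | 44% | 78% |
| 756 (three pairs) | 5% | 49% | 97% | >99% |
| 491 (three pairs, 65% response) | 5% | 35% | 88% | >99% |

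The plan gives no patient response rate. The 65% is an assumption, equal to the rate the protocol reports for a previous provider survey.

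The shift at which a significant result is as likely as not is 1.96 × SE: 1.96 × 0.0891 = 0.17 SD for one pair and 1.96 × 0.0514 = 0.10 SD for three pairs. Pooling waves makes the test more sensitive to such a shift and does not average it out.

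**The case against.** The case against has real force on several points.

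- **Same CHW.** The text speaks of the CHWs in general. That the patient's own coach asks the 12-month questions is an inference from the pairing. It stands as likely in many cases, but not as a stated rule.
- **Amount of contact.** Sessions are offered, contact is limited to what patients accept, and those not ready to engage are re-called only every 6 months. Some patients will know the CHW little at 12 months.
- **Direction.** A reader might infer that rapport must inflate the follow-up scores. The documents do not support that. The intake caller is also a CHW, introduced by letter on the PCP's behalf, so favourable answering can occur there too, and familiarity might make answers franker.
- **Magnitude.** Any systematic shift of the same size at the same n gives the same rejection rates. They show sensitivity, not that a bias exists.
- **Mode.** Some surveys may be self-completed, given the references to returned and mailed forms. This is an unreconciled conflict. Uncontrolled mixing of modes would not remove the confounding.
- **Larger flaw.** The non-randomised comparator for survey outcomes remains whoever conducts the interview, and patients who know they were coached may answer favourably to anyone.

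The neutral-party sentence under Protection Against Risks does not answer the point. It defines neutrality by the employee's supervisory chain, which reads as a safeguard for staff. Whether a CHW counts as part of the health care team for the confidentiality statement is a matter of interpretation and is no evidence of bias.

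**Conclusion.** The concern holds in a limited form. As planned, any effect of answering to a familiar coach cannot be separated from the intervention effect on PAM and self-reported behaviours. This rests on the stated use of CHWs as interviewers, on intake as the time of the baseline survey, and on the inference that the 12-month interviewer will often be the patient's own coach.

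Its size and direction are unknown, and the 20%, 61% and 92% figures are conditional on assumed shifts. A reader might go further and conclude that the survey results will be biased upward, or that the trial's main results are compromised. Neither follows. The documents contain no evidence of a shift, and diabetes incidence and weight are taken from the EMR. The point deserves action because PAM appears among the primary hypotheses and the remedy is cheap.

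**What to change.** 1. Leave the intake survey and PAM with the assigned CHW, since the PAM guides the choice of coaching strategy and the CHW is then new to the patient.
2. Have the 12-month survey done in the same live mode by an existing CHW who did not coach that patient, language-matched where possible, or by existing project staff. Project staff are preferable, because another CHW still belongs to the programme being judged.
3. Withhold the 12-month answers from the coach.
4. Record mode and interviewer for every survey.
5. Reconcile Patient Data (CHW-administered) with Data Storage and Confidentiality and the consent section (returned or mailed surveys).

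A mailed form as the first approach at 12 months is not advised. It would add a mode difference from the live intake call.

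**Cost.** Protocol wording and reassigned calls. With five CHWs and 252 patients per wave, about 252 / 5 ≈ 50 follow-up calls per CHW would be exchanged, with none added. With two CHWs at each site and one shared, each site has two who did not coach a given patient, though the plan does not state their languages. The 12-month response may fall slightly. Swapping CHWs reduces the problem without eliminating it, and the non-randomised comparator needs its own remedy.
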